#### Secondary Objectives:

- 1) Investigate if there is a difference in surgeon assessment of surgical exposure when performing surgery under deep vs. moderate NMB
- 2) Investigate and compare various exploratory endpoints between deep and moderate NMB. These endpoints include: the total dose of analgesics during the procedure, the total dose of analgesics

postoperatively, postoperative shoulder pain, total intraoperative blood loss, operating time, postoperative nausea, time to the first *postoperative* antimetic, total dose of antiemetics postoperatively, and postoperative RASS scores (Richmond Agitation Sedation Scale)

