#### Secondary Hypotheses:

- 1) Deep NMB will result in improved surgical exposure (assessed by the surgeon) during robotic surgery
- 2) There will be an improvement in outcomes of various exploratory endpoints as a result of deep NMB. These endpoints include: the total dose of analgesics during the procedure, the total dose of analgesics postoperatively, postoperative shoulder pain, total intraoperative blood loss, operating time, postoperative nausea, time to first *postoperative* antiemetic, total dose of antiemetics postoperatively, and postoperative RASS scores (Richmond Agitation Sedation Scale)

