#### Standardization of Anesthetics:

General anesthesia will be induced as per department routine with minimal variation on induction and maintenance of anesthesia. Upon arrival to the operating room (OR), standard ASA monitors will be applied before induction of anesthesia. All patients will be induced with midazolam (2 mg), propofol (2 mg/kg), fentanyl (1 mcg/kg), lidocaine (1mg/kg), and rocuronium (0.45 mg/kg). This anesthetic regimen will be standardized for both the moderate (control) and deep (intervention) NMB arms.

Patients will receive 100% oxygen during induction of anesthesia. After induction, anesthesia will be maintained at an age-adjusted minimum alveolar concentration (MAC) of 1 with sevoflurane. This will be titrated to maintain a Bispectral index of 35-55. Ventilation will be maintained with tidal volumes of 7 ml/kg, FiO2 less than 50%, and positive end-expiratory pressure (PEEP) and respiratory rate aimed towards normocapnia (ETCO2 of 35-45). For all patients in both arms of the study, two antiemetics (Dexamethasone 4 mg and Ondansetron 4 mg) as well as intravenous acetaminophen (1000 mg) will be administered.

Patients with rapid sequence inductions with succinylcholine will be excluded from participation. If a rapid sequence induction is conducted with rocuronium, the patient will have to demonstrate the start of recovery  $\mathbf{q}$ 

even if the rocuronium dose exceeds 0.45mg/kg. The first sign of the start of recovery from neuromuscular blockade is defined as either the presence of a single twitch on TOF, or a post tetanic contraction of 1 or higher.

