#### Postoperative pain (primary endpoint) and postoperative shoulder pain (exploratory endpoint):

The numeric pain scale (NPS) is a subjective measure which can be used in recovery rooms to assist in the assessment of pain. Individuals rate their pain on an eleven-point numerical scale. The scale is composed of 0 (no pain at all) to 10 (worst imaginable pain). Postoperative pain scores are assessed by PACU nurses according to the following scheme:

As per Post Anesthesia Care Unit (PACU) standard of care at Josie Robertson Surgery Center, the PACU nurses that have been trained by the PI and blinded to randomization will ask the patient to rate their pain. The actual question asked is, "on a scale from 0-10, where 0 is no pain and 10 is excruciating pain, please rate

your pain." The pain assessment is administered verbally. PACU nurses ask the patient to rate their pain utilizing the NPS scale. The PACU nurses will be evaluating and assessing pain per the Josie Robertson standard of care by using the Post Anesthetic Discharge Scoring Tool (see Appendix 8). Hour 1 pain scores will be captured from the nursing PACU electronic flowsheet.

Hour 6 and 12 pain scores will be captured in the research assessment form (see Appendix 2).

Most patients on this study will be discharged before 24 hours so assessment at the 24 hour and 48 hour time points will be completed via telephone by the research staff. In the event that the patient has not been discharged from PACU at 24 and 48 hours, the pain scores will be captured in person on the research assessment form.

The 24 and 48 hour time points will be recorded as close to 24 and 48 hours as possible with a +/- 8 hour window to allow for difficulties in reaching patient (see Appendix 2).

Postoperative shoulder pain will be defined at postoperative times of 1-hour, 6-hour, 12-hour, 24-hour and 48-hour on the research assessment form. A pain scale of 0-10 will be utilized (0 = no pain, 10 = worst pain imaginable)

PACU TIME is defined as time of patient arrival to PACU.

Additionally, the total dose of analgesics will be recorded during the intraoperative and the postoperative periods until patient discharge.

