#### 6.2 Subject Exclusion Criteria

1. Age younger than 18.

- 2. Inability to provide informed consent.
- Allergy to rocuronium, sugammadex, midazolam, propofol, fentanyl, lidocaine, mannitol (IV Acetaeminophen), IV Acetaminophen, Ketorolac, Morphine, Hydropmorphone, Dexamethasone, Zofran, Bendaryl, Compazine
- Neuromuscular disease.
- 5. Any patient with previous abdominal surgery less than or equal to 20 years prior to scheduled surgery date.
- 6. Patients with BMI> 35.
- 7. Severe renal impairment (creatinine clearance <30 ml/min).
- 8. Pt receiving Toremifene or any history of receiving Toremifene.
- 9. Chronic pain patients.
- 10. Patients receiving suboxone.
- 11. Patients receiving succinylcholine.

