Although the occurrence will probably be rare, accidental unblinding will be recorded as a protocol violation as part of standard reporting procedure. According to the ICH E9 Statistical Principles for Clinical Trials, usually of violations that occur post-randomization, it is appropriate to include the data from such subjects in the analysis, consistent with the modified intention-to-treat principle. We will include these cases in the primary analysis of the primary outcome in the randomized arm. For each case of major protocol violation, we will enroll an additional patient randomized and included in the analyses. Also, we will perform per protocol analysis that excludes patients who had accidental unblinding.

Surgeon assessment of surgical conditions (continuous measure, on a 1 to 5 scale) recorded every 30 minutes, will be analyzed with linear mixed-effects models as above.

Estimated blood loss (EBL) will be compared between the two arms using linear mixed-effects model (randomized arm and BMI fixed-effects variables, and surgeon-level random effect), accounting for duration of surgery if necessary (i.e., rate of EBL). Transformation of the outcome may be applied if the normality-of-errors assumption is violated.

Postoperative pain (surgical and shoulder pain, 0 no pain to 10 worst pain imaginable), defined at postoperative 1-hour, 6-hour, 12-hour, 24-hour, and 48-hour post operation will be compared between the two arms using linear mixed-effects models with appropriate transformation for the outcomes for normality.

The model will include patient-level random effects (nested within surgeons), treatment arm, and time as fixedeffects, along with stratification variable (BMI) as adjustment factors. To address potential confounding due to history of chronic pain, patients with chronic pain will be excluded from protocol. Chronic pain will be defined as a patient on a sustained-release opioid in the last 3 months. Besides patient-reported pain scores, perioperative analgesia use will be analyzed similarly to the pain scores: intraoperative cumulative IV analgesia use will be compared between the two arms after adjusting for duration of surgery; while postoperative IV analgesia use will be analyzed as cumulative total dose within the first 6-hours post surgery and until prior to discharge (with adjustment for duration of postoperative stay in the analysis).

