#### **DATA TO BE COLLECTED**

- Name
- MRN
- · Date of birth
- Date of operation
- Sex
- ASA status
- Race
- Height
- Weight
- BMI
- Comorbidities
- Preoperative Medications/Intraoperative Medications/Postoperative Medications
- · Rocuronium infusion rate
- Sugammadex dose
- IAP recorded every 15 minutes & additional time points, if applicable
- Surgical Assessment (Leiden scale) recorded every 30 minutes
- Volume and types of fluids intraop, including blood products
- Estimated blood loss
- Surgery start and end times
- Stage of disease
- Grade 3 or greater complications as described according to the MSKCC Graded Postoperative Complications Criteria
- Cause of death (if known)
- LOS
- Postoperative pain (surgical and shoulder) and nausea at postoperative time points
- Surgeon assessment of arm to which their patient was assigned
- RASS scores
- All requests by surgeons to vary IAP (independent of actual change in IAP)
- Gabapentin Pre-Operative and Post-Operative dose
- Position of electrode on wrist (collected by an MSK managed device in the OR)
- NPS scores

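### Section 14 analyses only intravenous analgesia, with no common unit, although the objectives and data collection cover the total analgesic dose by any route

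*Combined protocol and SAP*

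**What the plan says.** **Endpoint.** Section 2.0 lists among the exploratory endpoints "the total dose of analgesics during the procedure, the total dose of analgesics" given postoperatively. The Secondary Hypotheses repeat "the total dose of analgesics postoperatively". Neither restricts the route.

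**Data.** Section 4.1 (Postoperative pain) states that "the total dose of analgesics will be recorded during the intraoperative and the postoperative periods until patient discharge", and Section 12.0 says the same. The list of data in Section 16.0 includes preoperative, intraoperative and postoperative medications, and separately "Gabapentin Pre-Operative and Post-Operative dose".

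**Analysis.** Section 14.0 says that "intraoperative cumulative IV analgesia use will be compared between the two arms after adjusting for duration of surgery", and that "postoperative IV analgesia use will be analyzed as cumulative total dose within the first 6-hours post surgery and until prior to discharge", the latter with adjustment for length of postoperative stay. Analgesic use is to be analysed in the same way as the pain scores, for which a transformation is allowed.

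**Agents.** Under the standardised anaesthetic every patient receives fentanyl at induction, and "intravenous acetaminophen (1000 mg) will be administered". The allergy exclusion in Section 6.2 lists "IV Acetaminophen, Ketorolac, Morphine, Hydropmorphone, Dexamethasone, Zofran, Bendaryl, Compazine", so ketorolac, morphine and hydromorphone are evidently foreseen. No unit, equivalence conversion, opioid/non-opioid split or by-drug analysis is stated.

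**The concern.** The analysed variable is narrower than the endpoint it is meant to address, and the plan gives no reason for the narrowing. Any analgesic given by another route is collected and then adds nothing to the result. For the IV drugs that remain, a single cumulative dose cannot be computed across different agents until someone chooses a unit. If that choice is made after unblinding, the result is open to analyst discretion.

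This matters more than an exploratory label suggests, because pain over the first 6 hours is a co-primary endpoint. As Section 14.0 specifies it, the AUC model for pain contains arm, BMI and random effects. It has no term for rescue and no rule for scores taken after rescue. If patients in both arms are treated until their scores are similar, a benefit of deep block would show mainly as less analgesic use. The analgesic analysis is the only planned one that could show it. Antiemetics, which support no primary endpoint, are treated more fully: Section 14.0 plans any-use, time-window and time-to-first-rescue analyses for them, with no IV limit.

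**Working it through.** The plan attaches no figure to the analgesic analysis, so there is none to reproduce. The sample-size calculation concerns the two primary endpoints and does not bear on this point.

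**Step 1: scope, side by side.**

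| Place | Period | Route |
|---|---|---|
| Section 2.0, objectives and hypotheses | during and after surgery | not limited |
| Sections 4.1 and 12.0, recording | during surgery, and after surgery to discharge | not limited |
| Section 16.0, data list | before, during and after surgery | not limited |
| Section 14.0, analysis | during surgery; 0-6 hours; to discharge | IV only |

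Only the analysis section restricts the route, and no other analysis is named for what it leaves out.

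**Step 2: when the restriction biases the comparison.** Let r be the true ratio of total analgesic use, deep over moderate, in any common unit. Let f_m and f_d be the non-IV shares in the moderate and deep arms. The IV-only analysis then estimates

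observed ratio = r × (1 − f_d) / (1 − f_m).

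The documents give neither share. The values below are assumptions chosen to show the range.

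| True ratio r | f_m | f_d | Calculation | IV-only result for deep block |
|---|---|---|---|---|
| 1.00 | 20% | 20% | 0.80/0.80 = 1.00 | no difference (correct) |
| 1.00 | 20% | 40% | 0.60/0.80 = 0.75 | 25% lower |
| 1.00 | 40% | 20% | 0.80/0.60 = 1.33 | 33% higher |
| 0.80 | 40% | 20% | 0.80 × 0.80/0.60 = 1.07 | about 7% higher |

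With equal shares the relative comparison is unbiased, although the absolute amount is understated. With unequal shares the error can run in either direction, and in the last row it reverses a true 20% reduction.

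**Step 3: which window is more exposed.** The to-discharge window runs on after the first 6 hours, so it leaves more time for non-IV drugs. The 0-6 hour window, which matches the primary pain endpoint, may be mostly IV. This is a judgement; the documents contain no data on it.

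**Step 4: the unit.** If two drugs differ in potency per mg by an assumed factor R, equally effective doses differ R-fold in a raw mg sum: 5-fold for R = 5, 50-fold for R = 50. A cumulative dose across agents therefore needs either a stated conversion or separate reporting by drug. The plan gives neither.

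**The case against.** The strongest reply is that this is a wording mismatch in an exploratory endpoint. No success, futility or safety rule uses analgesic dose. The data are collected in full, so an all-route summary remains possible at reporting. Patients and endpoint assessors are blinded, so the route should not depend on arm except through pain itself. All of this stands, and it limits the weight of the point. The exception for pain matters, however: if deep block does reduce pain, patients may leave IV drugs at a different time, and the shares then differ in the very case the trial hopes to see.

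Several stronger readings are tempting and are not supported:

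- *Raw milligrams of unlike drugs are summed.* The plan does not say so. It is silent on the unit, and a by-drug or equivalent-dose total would also fit its words.
- *Acetaminophen swamps the total.* Taking 1000 mg against fentanyl at 1 mcg/kg and an assumed 80 kg (0.08 mg) gives 1000/0.08 = 12,500. Both are protocol-standardised intraoperative doses, and the same 1000 mg in every patient cancels from an untransformed arm difference. It would not cancel after a log transformation, but that still presupposes a raw sum.
- *A patient moved to oral drugs scores zero.* The dose is cumulative, so IV doses before the move still count. Only a patient who never received IV analgesia scores zero.
- *A large share of rescue is non-IV.* No share is given. Gabapentin is listed without a route and is not described as rescue. The content of Appendix 2 is not in the text.
- *The pain result could not be interpreted.* It remains interpretable as pain under usual care, and the IV analysis remains a partial check on rescue.

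**Conclusion.** The point holds in a limited form. Section 14.0 confines the analgesic analyses to IV drugs in all three periods, while the stated endpoint and the recorded data have no route limit. It also states no unit for combining agents. Both follow from the text and need no assumption.

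The size of the effect cannot be computed. The 25%, 33% and 7% figures rest on assumed shares and show only that unequal non-IV shares can create, hide or reverse a difference; equal shares leave the ratio unbiased. The primary analyses are not invalidated. What is weakened is the one planned comparison that would help a reader see whether similar or lower pain scores came with more or less analgesic. The change should be made because it is cheap and closes an open choice before unblinding.

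**What to change.** In Section 14.0, replace IV analgesia use with total opioid by all routes, expressed in morphine equivalents, for the intraoperative, 0-6 hour and to-discharge periods. Name one conversion table and fix it before unblinding. Report non-opioids (acetaminophen, ketorolac, gabapentin) separately by drug rather than adding them to the opioid total.

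The cost is a few lines of text and a conversion step in the analysis program. The protocol already provides for recording analgesic doses and postoperative medications, so neither data collection nor patient treatment changes. The one downside is that results depend on the chosen conversion table; fixing it in advance removes the analyst's discretion but not that dependence.

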#### 14.0 BIOSTATISTICS

In this single-blinded prospective randomized study, patients will be randomized in 1:1 ratio to two arms: moderate NMB (control) or deep NMB (intervention). The two primary endpoints of interest in this study are: levels of IAP and postoperative pain. Thus, in the sample size calculation below, we consider multiple primary endpoints and power the trial to detect success in at least one endpoint. The first primary endpoint of interest is IAP. The second primary endpoint of interest is Pain scores within 6-hours post operation. To characterize the entire set of a patient's IAP measurements under insufflation, we consider the use of area under the curve (AUC). We plan to randomize 130 patients to moderate or deep NMB arms, stratified by BMI (< vs >=30) and surgeon, and expect 120 patients to be evaluable for each of the two primary endpoints. Patients are considered evaluable for the first primary endpoint (IAP) if they can provide at least one IAP recording; patients are considered evaluable for the second primary endpoint (Pain) if they can provide at least one NPS pain score within the 6-hours postoperation.

AUC is a useful clinical endpoint for the aggregate effect over time and can summarize the average response to treatment over the period of observation. AUC is an appropriate summary measure for data collected over time, and it is commonly seen in pain measurements, as well as chronic obstructive pulmonary disease (COPD), diabetes, and pharmacokinetics studies. For this study, we will use the area under the IAP curve during insufflation as a measure for the first primary endpoint which focuses on the effect of deep NMB on IAP during robotic prostactetcomy. We will consider the time-weighted measure of AUC that integrates serial

2.1

assessments of the patient's IAP measurement over time using the trapezoidal rule. The corresponding "mean AUC" (AUCmean) is obtained as AUC/duration of insufflation for each patient. From **Kim et al**, mean IAP decreased by approximately 22% (standard deviation [SD] = 1.3) from moderate NMB to deep NMB.

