For the second primary endpoint based on postoperative pain, we will collect all NPS pain scores within the 6-hours postoperation and will express results as AUCpain at the patient level. In a retrospective analysis of 37 patients from a similar population (See Section 3.8), mean pain level within the 6-hours postoperation was 1.3 (SD of 0.5) on the **log-transformed NPS scale**.

Sample size calculation is based on the mean AUCIAP and AUCpain within 6-hours postoperation across patients in each arm. We power this study with 2 primary endpoints to detect 20% decrease in IAP (from 13.9 to 11.1, SD of 4) and 25% decrease in pain scores within the 6-hours postoperation (from 1.3 to 0.975; SD of 0.5) with deep vs moderate NMB, with type I error rate of 0.025 for each endpoint. The change in NPS scores (25% or 1 point on the raw scale) is a validated clinically meaningful change. The decrease in pain scores on which the sample size estimate is based on the natural log transformed scores. This calculation assumes independence of the two primary endpoints. We elected to increase the standard deviation of the AUCIAP in this power calculation as a conservative measure because the population from the reference study is different from the population of interest. A total of 120 patients evaluable for each of the primary endpoints will provide 90% power to detect a significant difference in at least one of the two endpoints. This sample size also allows for an interim analysis halfway through enrollment, using O'brien-Fleming boundaries with Lan de Mets spending functions for futility. We base the interim analysis decision rule on both of the primary outcomes. The trial will continue to full enrollment if the interim analysis results for either/both of the primary outcomes reports p<0.755. The trial may be terminated if p>0.755 for both outcomes. We will conclude that the arms are significantly different if p≤0.025 for either of the outcomes. In order to ensure at least 120 patients evaluable for each of the primary endpoints, we plan to randomize at least 130 patients (See Section 13.0 for potential perioperative scenarios).

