Analysis of the primary endpoint which involves IAP will be AUCIAP compared between the two arms using the linear mixed-effects model: randomized arm as the fixed-effect, BMI as the adjustment covariate, with surgeon-level random effects. Transformation of the outcome may be applied if the normality-of-errors assumption is violated. As a secondary analysis, the longitudinal IAP measurements will be analyzed using linear mixed-effects models including time and randomized arm as fixed-effects with stratification variable (BMI), and patient-level random effects, nested within surgeons. In the rare case that the patient's IAP is beyond 15 the surgeon will be unblinded to the IAP, and only the IAP up to the point of unblinding will be included in the analysis. 15 is the conventional goal for the upper limit of IAP at MSKCC. Investigators request they know the IAP at a level of 15, so they can weigh risk/benefit of continuing to operate at that higher threshold of IAP. In this rare occurrence, patients will still be included in the analyses as modified intent-to-treat, including IAP values until IAP-unblinding.

Analysis of the second primary endpoint will be AUCpain within 6-hours postoperation. AUCPain analysis will be conducted with linear mixed-effect model with appropriate transformation for the outcome for normality. The model will include randomized arm as fixed-effects along with stratification variable (BMI), and patient-level random effects, nested within surgeons.

For the primary analyses, all recorded IAP will be analyzed in a modified intent-to-treat fashion. Where a patient randomized to moderate NMB crosses over to deep NMB, all recorded IAP will be analyzed under the randomized arm. As a secondary analysis of the primary outcome, we will perform an as-treated analysis where the set of IAP values will be assigned to the actual intervention received. Correlation between AUCIAP and AUCPain will be summarized using Spearman correlation coefficient. Additionally, the primary endpoints will be summarized between patients with and without neuromonitoring issues (see

Section 13.0). As a sensitivity analysis, planned analyses of both primary endpoints will be repeated after excluding patients with neuromonitoring issues (see Section 13.0).

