Postoperative nausea (measured at the same intervals) will also be analyzed with linear mixed-effects models. To address potential confounding due to preoperative risk for nausea, the model will include adjustment for preoperative Apfel score (4 point scale with a maximum of 3 points due to an all male patient population) and preoperative EMEND use. In addition to patient-reported nausea scores, postoperative antiemetic use will be analyzed in the following fashion: the use of any antiemetics will be analyzed with a mixed-effects logistic regression model, and the use of any antiemetics within the first 6-hours post surgery and until prior to discharge will be analyzed with linear mixed-effects models. Time to first rescue antiemetic medication will also be recorded and compared between the two arms using Kaplan-Meier approach and log-rank test.

We will assess the relationship between the treatment arms and operating time (defined as the time between incision to surgery end) using a linear mixed-effects model with transformation for the outcome for normality. The model will include treatment arm and stratification variable (BMI) and surgeon-level random effect

Richmond Agitation Sedation Scale (RASS) scores, measured at 1, 6, 12, 24 hours postperatively will be modeled and compared between the two arms using linear mixed-effects model. The model will include treatment arm and stratification variable (BMI) and surgeon-level random effect.

One primary concern from deep paralysis is postoperative pulmonary complications and the need for reintubation and prolonged postoperative intubation. All patients who receive neuromuscular blockade are at 23

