#### 15.2 Randomization

The study will be conducted in a prospective randomized fashion. We plan to randomize 130 patients in 1:1 ratio to ensure at least 120 patients would be evaluable for each of the two primary endpoints. During the registration process, research staff will complete a protocol-specific Eligibility Checklist. After consent is obtained and eligibility is established, patients will be registered as described in Section 15.1.

After successfully registering the subject, the research study staff will randomize them in CRDB (Clinical Research Database) stratified by BMI (<30 vs ≥30) and surgeon. Only the anesthesia research team (CRM and CRCs) and the anesthesia care team in the OR will have access to the arm assignments.

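### Time to first rescue antiemetic is tested without the randomisation strata; if surgeon or BMI predicts antiemetic use, that test is conservative and loses some power

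*Combined protocol and SAP*

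**What the plan says.** Section 14.0 describes the allocation as "stratified by BMI (< vs >=30) and surgeon", and Section 15.2 repeats it as "stratified by BMI (<30 vs ≥30) and surgeon". The size is given in Section 15.2: "We plan to randomize 130 patients in 1:1 ratio to ensure at least 120 patients would be evaluable".

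The plan then carries these factors into most of its models. The primary IAP analysis has "BMI as the adjustment covariate, with surgeon-level random effects". The pain models use BMI and patient effects nested within surgeon. Blood loss has BMI and a surgeon random effect. For operating time, and again for RASS, Section 14.0 says "The model will include treatment arm and stratification variable (BMI) and surgeon-level random effect".

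Time to first rescue antiemetic is the exception. It is to be "compared between the two arms using Kaplan-Meier approach and log-rank test". No stratum, covariate or supporting Cox model is named, and no reason is given for the difference.

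The endpoint appears in Section 2.0 under the secondary objective to "Investigate and compare various exploratory endpoints between deep and moderate NMB". It has no power statement and no significance level of its own; the only level in the plan is for the two primary endpoints, "with type I error rate of 0.025 for each endpoint".

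**The concern.** Stratified allocation keeps the arms balanced within each BMI-by-surgeon group. If those groups differ in how soon patients need an antiemetic, the balance makes the observed-minus-expected difference between arms less variable than it would be under simple randomisation. The ordinary log-rank variance does not know this, because it treats all patients at risk as exchangeable. The test statistic is then divided by too large a standard error, so it rejects too rarely under the null and has less power under an alternative.

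At stake is efficiency on one exploratory endpoint, plus agreement with the plan's own convention. There is also a practical gap: Kaplan-Meier curves and a log-rank test give no hazard ratio. Because the text is silent, the analyst could also choose between a stratified and an unstratified test after seeing the data.

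**Working it through.** The documents state no event count, hazard ratio, power or significance level for this endpoint, so there is no plan figure to reproduce. The size of the effect has to be simulated.

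**Inputs from the documents.** 130 patients, 1:1, stratified by BMI (<30 vs ≥30) and surgeon.

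**Assumed, because the documents do not give them.** 4 or 8 surgeons (extended to 10 below); 30% of patients with BMI ≥30; permuted blocks of 4; baseline antiemetic use of 30% or 60%; hazard ratio 0.5 for power; two-sided 5% level; exponential times with administrative censoring. Strength of the strata is given as the surgeon SD on the log-hazard scale and the BMI hazard ratio: none (0; 1), weak (0.3; 1.25), moderate (0.5; 1.5), strong (1.0; 2.0).

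**Statistics.** Unstratified: Z = (O − E)/√V over all patients. Stratified: Z = Σ(O − E)/√ΣV, summed over BMI-by-surgeon cells. Reject if |Z| > 1.96.

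**Precision.** With 8,000 replicates the Monte Carlo standard error is √(0.05 × 0.95/8000) = 0.24 points at 5% and at most √(0.25/8000) = 0.56 points for power.

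**Results at 60% baseline use** (unstratified / stratified on all cells):

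| Surgeons | Strata | Type I error, % | Power, % | Change in power, points |
|---|---|---|---|---|
| 4 | none | 5.1 / 5.2 | 78.1 / 77.1 | −1.0 |
| 4 | weak | 4.6 / 5.2 | 78.2 / 78.5 | +0.3 |
| 4 | moderate | 3.9 / 4.8 | 76.3 / 79.5 | +3.2 |
| 4 | strong | 2.3 / 5.5 | 62.6 / 79.0 | +16 |
| 8 | none | 5.0 / 4.8 | 76.8 / 74.0 | −2.8 |
| 8 | weak | 4.5 / 5.1 | 78.0 / 75.8 | −2.2 |
| 8 | moderate | 3.7 / 5.1 | 75.6 / 76.5 | +1.0 |
| 8 | strong | 2.3 / 5.3 | 61.2 / 77.7 | +16 |

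At 30% baseline use the pattern is the same, with changes of −0.4 and −1.6 (none), +0.1 and −0.7 (weak), +2.1 and +0.6 (moderate), and +11.6 and +10.8 (strong) for 4 and 8 surgeons.

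**Cause.** With strong strata and 8 surgeons but simple randomisation, the unstratified test rejects 5.2% of the time. The shortfall therefore comes from stratifying the allocation and not the test. A rejection rate of 2.3% corresponds to |Z| > 2.27 for a standard normal, so the actual SD of the unstratified Z is about 1.96/2.27 = 0.86 instead of 1.

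**Wider range.** A second set of runs (3,000 replicates) gave unstratified type I error of 4.4% to 5.3% (none), 3.3% to 4.3% (moderate) and 1.8% to 3.4% (strong). Full stratification gained about 2 to 6 points with moderate strata and 8 to 15 with strong, and lost up to about 5 points with non-prognostic strata and 10 surgeons. The bounds of the two sets differ by a few points, so the ranges should be read as approximate.

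**Which factor matters.** In the strong scenario with 8 surgeons and 60% use, stratifying by BMI alone raised power only from 61.2% to 62.8%. Surgeon carries most of the variation in these scenarios, so a fix confined to BMI would recover little.

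**The case against.** The strongest case against runs as follows. The loss exists only if surgeon or BMI predicts antiemetic use, and the documents give no data on that. The nausea risk factors that the protocol names are the Apfel items and preoperative EMEND (Section 4.1, Postoperative nausea; Section 14.0). The anaesthetic and two prophylactic antiemetics are standardised in both arms (Section 4.1), which makes a large surgeon effect less likely. The all-male population and prophylaxis may also leave few events. In runs with 15% baseline use and fairly strong strata (surgeon SD 0.6, BMI hazard ratio 1.5), power moved only from 29.5% to 30.9% with 6 surgeons and from 29.4% to 29.9% with 10. Antiemetic use is also covered by mixed-effects models, and the endpoint decides nothing.

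Most of this stands, and it limits the size of the point. It does not remove it. The protocol's own argument gives surgeon a possible route: the surgeon controls IAP (Section 3.0, Summary), and nausea is said to worsen with rising IAP (Section 3.6). That supports plausibility, not magnitude.

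Three stronger readings are tempting and are not supported:

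- A reader might infer that the test is invalid or inflates type I error. It does neither; in every scenario it was at or below 5% within simulation error.
- A reader might infer that the test is certain to be conservative. With non-prognostic strata it has its nominal size.
- A reader might infer that stratifying is free, or that sparse cells do no harm. With null strata, 60% use and 10 surgeons, full stratification took power from 77.0% to 73.2% in one run, and the loss reached about 5 points in another.

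The text is also silent on stratification and does not rule it out. The plain reading is still the ordinary unstratified test.

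**Conclusion.** The point holds as a minor, conditional one. The plan stratifies allocation by BMI and surgeon, uses both factors in the models listed above, and leaves them out for time to first rescue antiemetic. If the strata are prognostic the planned test is conservative. Across the runs at 30% to 60% baseline use, full stratification would then add about 1 to 6 points of power with moderate strata and about 8 to 16 with strong ones. If they are weak or irrelevant, it would change power by about −3 to +1 or −5 to 0 points.

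These figures rest on assumed surgeon numbers, event rates, hazard ratio and strength of the strata, none of which the documents supply. The finding is one of efficiency and consistency on an exploratory endpoint. Neither primary conclusion is touched. It is a worthwhile tidy-up, not a correction that the trial depends on.

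**What to change.** In Section 14.0, replace the plain log-rank test for this endpoint with a log-rank test stratified by surgeon. Add a hazard ratio with confidence interval from a Cox model stratified by surgeon (or with a surgeon frailty) and with BMI as covariate. This matches how the other models treat the two factors and supplies the effect estimate that is now missing. Stratifying by surgeon alone avoids the very small cells that arise when surgeon is crossed with BMI.

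The cost is one sentence and no new data, since BMI and surgeon are already needed for randomisation. The statistical price is a power loss of up to about 2 points if the strata turn out not to be prognostic, compared with up to about 5 if every BMI-by-surgeon cell is a stratum and there are 10 surgeons. The choice should be recorded before outcomes are examined by arm.
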